6.3. Selection of subjects for the study

✓ Study population

Patients requiring first-line or repeat endodontic treatment and meeting the eligibility criteria described in the following paragraph will be able to take part in the trial.

Patients taking part in this clinical trial will not be able to take part in any other trial. However, there is no exclusion period at the end of this trial for participation in any other study.

✓ Inclusion criteria for patient selection.

The characteristics required for a patient to be included in the trial are:

- Men or women aged over 18 years,
- Patients requiring endodontic treatment on a single tooth, in accordance with the latest HAS
 recommendations; treatment may be first-line (ET) or repeat (ER), on a monoradiculated or
 pluriradiculated tooth.
- A patient who is geographically stable and/or regularly monitored by the practice, and who can be monitored for 2 years,
- Patients who have signed their consent form,
- Patients affiliated to a social security / insurance scheme (Art L1121-11 of CSP).

✓ Non-inclusion criteria for subject selection.

The following characteristics exclude certain subjects from inclusion in the trial:

Dental exclusion criteria:

- Patients with a formal contraindication to endodontic treatment,
- Patient with a known contraindication to the use of BioRoot™ RCS or PA1704 filling material: endodontic treatment on immature or provisional teeth, known hypersensitivity to any of the compounds in the formula.

Exclusion criteria related to participation in the clinical trial:

Patients meeting at least one of the following criteria cannot be included in the study.

These criteria are not contraindications to the use of a permanent root canal filling material, but the first 4 on the list are confounding factors known to negatively influence healing rates and prognosis:

- Endodontic treatment of a tooth with a calcified root canal,
- Endodontic treatment of teeth with suspected perforation,
- Patients with a non-stabilized systemic disease such as diabetes or thyroid disorders, or who are immunocompromized or have undergone radiotherapy of the jaw.
- Patients suffering from active non-stabilized and untreated periodontitis.
- Simultaneous participation in another interventional trial,
- Vulnerable subjects referred to in Articles L.1121-5 to 8 and L.1122-1-2 of the Public Health Code and Article 66 of Regulation (EU) 2017/745 on medical devices are excluded from the trial: Pregnant women, breast-feeding mothers, persons deprived of their liberty, hospitalized without consent or admitted to a health or social establishment for purposes other than research, minors, adults under legal protection (guardianship or trusteeship) or unable to express their consent, persons in emergency situations unable to express their prior consent.

✓ Time of enrolment.

Patients will be included after diagnosis of the need for endodontic treatment.

✓ Criteria and procedures for withdrawing a subject or interrupting his or her participation.

The criteria for premature termination of a person's participation in the trial are as follows:

- Withdrawal of patient consent,
- Investigator's decision (reason to be specified),
- Serious adverse event,
- Treatment failure with need for repeat treatment notified before the 24-month follow-up for patients treated with the BioRoot™ RCS filling material, or before the 5-year follow-up for patients treated with the PA1704 ready-to-use filling material,
- Subject lost to follow-up (see definition below*),
- Subject wrongly included (non-compliance with at least one major inclusion and/or exclusion criterion).

Subjects will be able to withdraw their consent and ask to leave the trial at any time for any reason.

The investigator may permanently discontinue a subject's participation for any reason that is in the best interests of the subject, particularly in the case of serious adverse events.

*Definition of Lost to follow-up: the patient is considered lost to follow-up and prematurely withdrawn from the study if he/she fails to attend the follow-up visits scheduled in the protocol (scheduled appointment or, in the event of impediment or cancellation, any other new appointment scheduled), and the investigating center has not heard from the patient, despite repeated attempts to organize and conduct the visit by the investigating center. A patient who is absent from a follow-up visit (at 6 or 12 months, for example) but who attends the end-of-study visit at 24 months is not considered lost to follow-up (this is an interruption of clinical follow-up; the primary criterion collected at 24 months is available).

If a patient is lost to follow-up, the investigator will contact the patient or a family member by telephone to obtain the information needed to close the patient's file (clinical trial completion form).

✓ Stopping all or part of the clinical trial

The reasons for temporary or permanent early termination of the trial are as follows:

- 1) decision of the Sponsor,
- 2) decision of the person directing and supervising the trial,
- 3) decision of the institution responsible for the trial.

✓ Procedures for the premature termination of a person's participation in the trial

If a patient withdraws prematurely from the OPTIFILL trial, the investigator must document the reasons as fully as possible.

Withdrawal from the trial can only take effect after confirmation by the investigator and the SLB Pharma CRO. Patient withdrawals from the trial are always permanent and patients cannot be included in the trial a second time (for treatment on another tooth, for example). Patients will not be replaced.

The early termination of the OPTIFILL trial will have no impact on the patient's care by his or her dental surgeon. The patient will continue to be monitored as usual by his/her dental surgeon.

In the event of premature termination of the clinical trial, information will be transmitted by the CRO to the competent authorities of each European Member State and to the Ethics Committees within 15 days.

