Retro-alveolar X-rays are taken with an angulator using the parallel planes technique; the **entire tooth should be visible in the image** (crown to apex, passing through the root). There are no other specific settings imposed for the devices.

The images will be converted to .jpg format, without filters, and anonymized before being uploaded to the eCRF.

✓ Procedures for replacing subjects, if necessary.

See Chapter 7.4

6.2. Medical devices under investigation (ready-to-use material PA1704) and comparator (BioRoot™ RCS powder-liquid material)

✓ Comparator Medical Device Description — BioRoot™ RCS:

The selected comparator MD was the BioRoot™ RCS permanent root canal filling material.

BioRoot™ RCS is a Class III implantable medical device for dental use manufactured by Septodont. BioRoot™ RCS is based on Active Biosilicate Technology (ABS). It is a mineral root canal cement composed mainly of tricalcium silicate, zirconium oxide and calcium chloride. It comes in the form of **two products (powder-liquid) that are to be mixed**. Clinical indications, contraindications, characteristics, instructions for use, warnings, storage and disposal procedures are detailed in the instructions for use (see Annexe 3).

Thus, the medical device under investigation (PA1704) and comparator device (BioRoot™ RCS) are 2 calcium silicate-based cements, which are used for the same endodontic indications but come in 2 different forms, as a powder-liquid mixture or as a ready-to-inject paste. The 2 medical devices are similar and the aim of this study is to show that the performance and safety of the new material are not affected by the change in presentation.

✓ Exposure to medical devices under investigation and comparator

Patients included in the study will randomly receive one of 2 filling materials, PA1704 or BioRoot™ RCS, to treat one tooth (one or more root canals depending on the type of tooth affected by pulpal disease). The medical device is administered (implanted) only once, on the day of the endodontic treatment. The material is implanted for the long term, as it is intended to seal the root canals permanently. It is not intended to be removed during the trial, nor after the end of the trial, except where the treatment has failed with an indication to restart treatment.

✓ List of any other medical devices or medicines to be used during the clinical investigation.

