The Per Protocol (PP) population is the entire mITT population that perfectly complied with the protocol. Thus, subjects with major protocol violations, including major false inclusions (see below), and subjects for whom the primary criterion was not available, will be excluded from the PP population.

Major enrolment breaches include:

- No signed consent,
- Enrolment of a vulnerable subject,
- Enrolment of a patient with a contraindication to endodontic treatment or a known contraindication to the use of BioRoot™ RCS or PA1704 filling material,

Major deviations from the protocol include:

- Error in allocating the medical device,
- Failure to comply with the procedure for using the medical device,
- · Coronal restoration procedure contraindicated or insufficient,
- · Lost contact,
- No performance data,

Particular care will be taken to describe any deviations from the protocol.

All major deviations will be validated by the coordinating investigator, ideally during clinical implementation and monitoring visits, or at the latest at the time of data review; the evaluation will be carried out blind to the data relating to whichever medical device was allocated and data collected after randomization.

It should be noted that non-compliance with the schedule of visits scheduled at 6, 12 and 24 months (with a tolerance of \pm 1 month) will be considered a minor deviation from the protocol; the same applies in the case of a coronal restoration carried out after more than 45 days.

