 - o Preoperative pain (symptomatic tooth at enrolment, preoperative VAS).

7.7.11. Handling missing, unused or erroneous data, including drop-outs and withdrawals:

No imputation method is planned. However, as stated above, patients with treatment failure at 6 or 12 months will be withdrawn from the study and will be considered to have treatment failure at 24 months.

7.7.12. Exclusion of certain information from the hypothesis tests, if relevant:

None.

7.7.13. In the case of multi-center investigations, minimum and maximum number of subjects to be included for each center:

Each center will include 22 to 24 patients with an indication for initial or repeat endodontic treatment. The number of repeat treatments may vary between centers, but will total 30% in the sample. Some investigators, because of their specialty in endodontics, will include a majority of patients with an indication for repeat treatment, whereas GP investigators will probably have more indications for first-line treatment.

8. Data management

Procedures for examining data, cleaning databases, issuing and resolving data queries:

See Chapter 6.6, Data quality and monitoring section.

Procedures for verification, validation and securing of the electronic clinical data systems, where applicable:

The data collected in electronic CRFs is recorded directly in an electronic database using ENNOV software and hosted on a secure health data server in accordance with current regulations. The data collected in the paper logbooks is entered by the CRO into the electronic database using ENNOV software.

Data retention:

See the Archiving section in Chapter 12.4.

9. Amendments to the clinical investigation plan

Requests for substantial modifications will be sent by the CRO, on behalf of the sponsor, to the relevant ethics committees for their opinion and to the competent authorities for authorization, in accordance with law 2004-806 of 9 August 2004 and its implementing decrees in force.

Similarly, non-substantial modifications will be sent for information.

An updated version of the amended protocol must be dated. This new version will be sent to the investigators.

The patient information leaflet should be amended if necessary.

10. Deviations from the clinical investigation plan

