The status of the SAE must be classified as follows:

- Resolved,
- Resolved with sequelae,
- In progress,
- Death.

The date on which the AE was resolved must be added; if the AE is still in progress, "Not Applicable" should be entered.

Following submission of the initial paper report form, the Investigator/Rapporteur must respond to any follow-up requests or queries from the Sponsor in relation to the SAE within the same timeframe as for the initial report. All the above contacts will be systematically copied on any exchanges concerning an SAE.

The Investigator must also report all SAEs in the eCRF by completing an AE form page.

If the SAE results in the patient being withdrawn early from the study, the Investigator must give details of the reason in the comments section of the initial paper declaration form.

2/ Follow-up declaration:

The Investigator must draw up a specific clinical report and complete and send the "follow-up SAE form" to the CRO and the sponsor within the same timeframe as mentioned above. Test results and hospital reports should be sent to the e-mail addresses listed in the 14.5 section. SAEs must be monitored until they are resolved or stabilized.

3/ After completion of the study:

All SAEs, whatever their relationship with the medical device or the protocol, occurring within 30 days of the last visit of each patient must be notified to the Sponsor in the same way as mentioned above. Any event occurring at any time after the end of the study for a subject who participated in the study and which could be related to the medical device under investigation in the opinion of the Investigator should also be reported to the CRO and the Sponsor.

14.2.6. Urgent safety problem

Any serious threat to public health (as defined in section 14.1) must be reported immediately to the sponsor (contact persons: See section 14.5).

14.2.7. Pregnancy

Pregnancies occurring after the date of signature of the informed consent and up to study discharge (whether early or not) will not be considered a serious adverse event insofar as no genotoxic effect of the medical device under investigation or comparator has been demonstrated; they will be recorded by convention in the AE pages of the eCRF.

14.2.8. Responsibility of the sponsor:

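### An unqualified serious-adverse-event criterion for ending participation can cost 24-month primary outcomes that could still be collected after a single implantation

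*Combined protocol and SAP*

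**What the plan says.** **Ending participation.** Section 6.3 introduces its list with "The criteria for premature termination of a person's participation in the trial are as follows". One entry is "Serious adverse event". It is not limited to device-related events or to events that prevent attendance, and it stands apart from a separate entry for the investigator's decision. A little further on, the section says "The investigator may permanently discontinue a subject's participation for any reason that is in the best interests of the subject" and gives serious adverse events as the leading example. Section 14.2.5 is also conditional: "If the SAE results in the patient being withdrawn early from the study". So are the general provisions that open section 14. Section 6.3 adds that withdrawal needs confirmation by the investigator and the CRO, and that "Patient withdrawals from the trial are always permanent".

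**Exposure.** Section 6.2: "The medical device is administered (implanted) only once, on the day of the endodontic treatment".

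**Analysis.** Section 7.7.4 puts the main analysis on the per-protocol (PP) set. Under section 7.6, "subjects for whom the primary criterion was not available, will be excluded from the PP population". The mITT set in section 7.6 requires at least one efficacy result at 6, 12 or 24 months. Section 7.7.11: "No imputation method is planned". The one exception is that failure at 6 or 12 months counts as failure at 24 months. There is no rule for withdrawal after an SAE.

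**The concern.** With a single implantation there is no continuing study treatment to stop, so ending participation ends visits, X-rays and active AE collection and nothing else. Read literally, the SAE entry in section 6.3 discards a 24-month outcome that many of these patients could still provide.

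A loss triggered by a serious event may be related to the outcome. If it removes future failures more often from the PA1704 arm, the comparison moves towards non-inferiority. The mITT analysis is only a partial check: a patient withdrawn before any 6-month result is in neither set, and a patient withdrawn later enters mITT with no rule for the missing 24-month value. The trial is the first use of PA1704 in humans (section 3.3), and its device-related adverse effects are listed as not known (section 14.4).

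**Working it through.** **1. The plan's own sample size.** Section 7.2 assumes 90% efficacy in both arms, a 13-point margin, one-sided alpha of 5% and 80% power (the power is confirmed in section 7.3).

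n = 2 × 0.90 × 0.10 × (1.645 + 0.842)² / 0.13² = 65.85, so 66 per arm. This reproduces the plan. Adding 20% gives 66 × 1.20 = 79.2, so 80 per arm.

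**2. Who is exposed.**

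| Situation of a patient with an SAE | PP primary analysis | mITT |
|---|---|---|
| Not withdrawn, attends at 24 months | Kept | Kept |
| Failure notified at 6 or 12 months | Counted as failure | Counted as failure |
| Withdrawn after a 6- or 12-month result, no failure notified | Excluded | Included, but no rule for the 24-month value |
| Withdrawn before any 6-month result, no failure notified | Excluded | Excluded |
| SAE after the 24-month visit (PA1704 extension) | Unaffected | Unaffected |

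Only the third and fourth rows are at issue.

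**3. Loss of precision.** Taking 20% off 80 leaves 64 evaluable per arm. Power = Φ(0.13 / √(2 × 0.09 / n) − 1.645). For n = 64 this is 79.0%. Losing 1, 2, 3 or 4 more per arm gives 78.4%, 77.9%, 77.3% or 76.7%. That is about 0.6 points of power per patient lost per arm, which is small.

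**4. Possible bias.** The documents give no SAE rate, so every count below is an assumption. The lower limit is L = (p_N − p_R) − 1.645 × √[p_N(1 − p_N)/n_N + p_R(1 − p_R)/n_R], where p is the efficacy rate, N is PA1704 and R is BioRoot RCS. Non-inferiority needs L above -13 points.

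*Example A: a trial close to the margin, losing PA1704 failures only.*

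| Failures, PA1704 v BioRoot RCS | Difference | SE | L |
|---|---|---|---|
| 9/66 v 6/66 (none lost) | -4.5 | 5.51 | -13.6 |
| 8/65 v 6/66 (one lost) | -3.2 | 5.40 | -12.1 |
| 7/64 v 6/66 (two lost) | -1.8 | 5.27 | -10.5 |

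The planned Dunnett and Gent test agrees. With rates constrained to differ by 13 points, p_N = (x_N + x_R − 0.13 n_R)/(n_N + n_R), where x is the number of successes, and p_R = p_N + 0.13. Then z = (observed difference + 0.13)/SE, with the SE taken at those rates. This gives 1.56, 1.85 and 2.15 against 1.645, so losing one failure is enough in this example.

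*Example B: remaining patients near 90% efficacy.* BioRoot RCS has 59/66 successes. Of 66 PA1704 patients, s have an SAE and would also fail.

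| s | PA1704 successes if excluded | L if excluded | PA1704 successes if counted as failures | L if counted |
|---|---|---|---|---|
| 1 | 58/65 | -9.0 | 58/66 | -10.6 |
| 2 | 58/64 | -7.4 | 58/66 | -10.6 |
| 3 | 57/63 | -7.6 | 57/66 | -12.4 |
| 4 | 56/62 | -7.8 | 56/66 | -14.1 |
| 5 | 55/61 | -8.1 | 55/66 | -15.8 |

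Here the conclusion changes only from s = 4.

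**The case against.** A reader might infer that every patient with an SAE loses the 24-month outcome, and that this favours PA1704. The documents support neither step.

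- **Exit is not clearly automatic.** The discretionary sentence in section 6.3, the confirmation step there and the conditional wording in section 14 all suggest that an SAE is a permitted reason for withdrawal. This stands. But the SAE entry is separate from the investigator's decision and unqualified, so the text supports both readings. Discretion also does not remove the problem, because the investigator is not blinded to the device.
- **Direction is not shown.** The SAE definition in section 14.1 covers any serious event in either arm, including general medical events unrelated to the tooth. Treatment failure from lack of effectiveness is expressly not an AE (section 14.2.1). That patients with an SAE are more likely to fail, and more so with PA1704, is an assumption. This stands.
- **Some of the overlap is already handled.** Failures notified at 6 or 12 months are carried forward. This stands and narrows the exposed group.
- **Safety data on the event are kept.** The Tolerance set includes all treated patients, AEs are followed to resolution, and SAEs are reported for 30 days after the last visit. This stands for the event itself. Active collection of new AEs nevertheless ends with participation (section 14, general provisions).
- **The broader cause is a PP primary analysis without imputation**, which affects every reason for withdrawal. True, but the SAE entry is one reason that the plan itself creates and can remove.

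**Conclusion.** The point holds as a conflict in wording with an avoidable and possibly informative loss attached. Section 6.3 contains an unqualified criterion beside discretionary text, and nothing provides for collecting the 24-month outcome after withdrawal for an SAE. The exposed group is limited to patients withdrawn before 24 months with no failure notified, and is probably small.

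The cost in power is slight. The possible bias cannot be sized or signed from the documents. The change from -13.6 to -10.5 points comes from a case chosen just beyond the margin. With counts near the planned efficacy it takes four PA1704 patients who both have an SAE and would fail. Both examples assume that all such losses fall in the PA1704 arm. This is a minor point, worth making because the correction is nearly free.

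**What to change.** 1. Reconcile the list in section 6.3 with the discretionary sentence there and with section 14, so that an SAE does not by itself end trial follow-up. Separate the end of data collection from any decision about care. Care decisions stay with the investigator.
2. Where the patient still consents and the investigator does not judge attendance contrary to the patient's interests, collect the scheduled 24-month examination, X-ray and AE data, and keep the patient in the analysis. Section 6.3 already reasons this way for patients who miss interim visits but attend at 24 months.
3. State in sections 7.6 and 7.7.11 how a missing 24-month outcome after an SAE is handled in the PP and mITT analyses, including events that make it unobtainable, such as death. One option is a sensitivity analysis that counts it as failure.
4. Report SAE withdrawals before 24 months by arm, with the last available efficacy result.

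The cost is protocol and SAP wording, one sensitivity analysis and one table. No visit is added, and the required 66 evaluable patients per arm does not change.

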6.4. Timetable for the clinical trial

The trial schedule is defined as follows:

- Duration of recruitment period: 9 months are to be set aside to enrol 160 subjects,
- Expected duration of participation for each subject: 24 months (± 1 month) for patients treated with the BioRoot™ RCS material, or 5 years (± 6 months) for patients treated with the PA1704 material,
- Total planned duration of the clinical trial: 5 years and 9 months.

From the first subject enrolled and on behalf of the sponsor, the CRO shall immediately inform the competent authorities in France (ANSM) and Belgium (AFMPS), as well as the relevant ethics committees, of the effective start date of the trial (Effective start date = date of signature of the consent form by the first person to take part in the trial).

The end of the trial corresponds to the moment at which participation by the last person to take part in the trial comes to an end. The end date of the trial will be sent by the CRO, on behalf of the sponsor, to the competent authorities and ethics committees within 90 days.

